All subjects with symptoms of RTI detected by active or passive surveillance contacts will be reviewed by the investigator as soon as possible and those based on any suspicion of difficulty in breathing, wheezing or parental concern seen within 24 hours (refer to Section 9.2). This will ensure prompt assessment of need for medical care.

All cases of RSV-LRTI will be considered as adverse events (AEs) of special interest (refer to Section 9.1.5) and will have to be reported within 24 hours to the sponsor, and notified to the IDMC (which is not blinded), together with full case details, within 48 hours upon sponsor becoming aware. In order to support this timely reporting, the investigator will make the diagnosis according to his/her medical judgment and locally-available diagnostic tests of RSV infections. Criteria for hospitalization are not protocol defined but based on the attending clinicians' judgment of medical need.

The IDMC will receive on a regular basis cumulative summary reports of the number of RSV infections (asymptomatic and symptomatic) and the proportion progressing to hospitalization in the vaccinees by group and the incidence of RSV-RTI, RSV-LRTI and severe RSV-LRTI according to standardized case definitions by group (refer to Section 4.1). The frequency will be initially monthly from the beginning of the RSV season and will be adapted based on the instruction of the IDMC (refer to Section 9.10.3). The objective of this intense monitoring of cumulative RSV-RTI data by the IDMC is to ensure that, if it occurs, ERD is detected early in the course of the study allowing enrolment to be stopped and thereby minimizing the number of infants exposed to the ChAd155-RSV vaccine.

The final analysis of the incidence of RSV-LRTI by group will be performed according to the standardized case definitions for clinical symptomatology and diagnostic test at sponsor's laboratory (refer to Table 6) ensuring consistency across sites.

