#### 9.1.5.2. RSV-LRTI

LRTI associated with RSV infection will be reported as an adverse event of special interest in an expedited manner. These will be detected through the surveillance for RSV-RTI (refer to Section 9.2).

[figure not shown]
To identify RSV-LRTI for the purpose of AE of special interest, the diagnosis should be based on the investigators' clinical judgment taking into account the clinical history, the examination, relevant medical investigations and within 24 hours of results of a locally-available diagnostic test for RSV. Of note the case definition presented in [Table 6](#) is based on a limited set of symptoms and signs and is designed for protocol specified analyses pooled across sites at study conclusion and should not be used for the purpose of reporting RSV-LRTI as an AE of special interest during the trial conduct.

In addition to report these cases as AE of special interest, the investigator should investigate the case according to the procedures for the surveillance of RSV-RTI (refer to Section 9.2) and document it in the eCRF. Of note a nasal swab should be taken for confirmatory and quantitative testing of RSV infection by the sponsor.

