**Figure 3 Decision tree for passive and active surveillance contacts**

 Active contacts will take place weekly during each RSV season and every month outside the RSV season. Passive phone contacts from the parents/LARs to the investigator will take place when symptoms occur.

 Refer to the SPM for signs and symptoms to be collected.

 RSV-A/B quantitative PCR on all specimens.

 RVP (Multiplex PCR) on all specimens RSV-A/B positive and on all cases of confirmed LRTI according to case definition presented in Table 6.

 For example, in the event that the subject requires urgent medical evaluation and care or has travelled to another location.

 In case of worsening of symptoms, optional sample if the previous specimen was RSV-positive, and mandatory if the previous sample was RSV-negative.

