**Refer to APPENDIX D for the symptoms and grading for assessment visits and worsening visits.**

### 9.2.1. Passive surveillance

All subjects' parent(s)/LAR(s) will be instructed to contact investigator/study staff in case of any new or worsened RTI symptoms (cough, runny nose or blocked nose) or in case of any new difficulty in breathing or wheezing. They will be also reminded to record the start date and the end date of the RTI symptoms on the RTI episode card.

- **If there is** any new difficulty in breathing, wheezing or parental concern, the investigator/study staff will schedule an assessment visit as soon as possible (refer to Section 9.2.4), but no later than 24 hours after the phone contact to ensure prompt assessment of the need for medical care.
- **If there is no suspicion** of difficulty in breathing, nor wheezing, nor parental concern, but there are any new symptoms of an RTI (cough, runny nose or blocked nose), the investigator/study staff will schedule an assessment visit as soon as possible (refer to Section 9.2.4), but no later than 72 hours after the phone contact. Performing the visit as soon as possible is important to assess the need for medical care, to ensure that early symptoms are captured, and also to collect an optimal nasal swab for the detection of RSV.
- All passive surveillance contacts will be documented in the eCRF.
- In the event that it is not possible to schedule an assessment visit, which may arise if the family has travelled, then the assessment visit page of the eCRF should be filled in as completely as possible using available medical records.

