### 9.2.3. Active surveillance

There will be contact between the investigator/study staff and subject's parent(s)/LAR(s) on a regular basis (weekly during the RSV season and every month outside the RSV season). If there has not been a contact through a clinic visit (i.e., Visits 1, 2, 3, 4, 5, 6\*, 7, 8), a passive surveillance contact (refer to Section 9.2.1), an assessment visit (refer to Section 9.2.4) or a surveillance for asymptomatic RSV infection (refer to Section 9.2.2), then the investigator/study staff will contact the subject's parent(s)/LAR(s). The active surveillance will be performed by phone, mobile phone or e-mail.

\* In countries where *Menveo* or Placebo is used as a comparator, no administration will be performed at Day 121 and therefore in those countries there will be no Visit 6 and it will be administered at the end of the first RSV season at Visit 7 (refer to Table 2 and Table 7).

During each active follow-up contact, the investigator/study staff will:

- Confirm with the subjects' parent(s)/LAR(s), if the subject has developed new RTI symptoms (cough, runny nose or blocked nose) and if he/she has developed any symptoms of difficulty in breathing or wheezing (during and between contacts).
  - **If there is** any new or on-going difficulty in breathing, wheezing or parental concern, the investigator/study staff will schedule an assessment visit as soon as possible (refer to Section 9.2.4), but no later than 24 hours after the contact to ensure prompt assessment of the need for medical care.
  - **If there is no suspicion** of difficulty in breathing, nor wheezing, nor parental concern, but any new symptoms of an RTI (cough, runny nose or blocked nose) are present, the investigator/study staff will schedule an assessment visit as soon as possible (refer to Section 9.2.4), but no later than 72 hours after the contact.
- Performing the visit as soon as possible is important to assess the need for medical care, to ensure that early symptoms are captured, and also to collect a nasal swab for the detection of RSV.
- The investigator/study staff will remind subjects' parent(s)/LAR(s) to record the start date and the end date of the RTI symptoms on the RTI episode card.
- All active surveillance contacts will be documented in the eCRF.

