#### **9.2.4. Assessment visit**

The purpose of the assessment visit is to objectively document signs and symptoms by an appropriately qualified person (i.e., medical or nursing), provide medical advice and to take a nasal swab for detection of RSV infection.

- Assessment visits may take place in the subject's home, the investigators clinical facility or a medical facility as appropriate to the circumstances in the judgment of the investigator.
- If the reported symptoms are already of a level of severity that urgent care is indicated, the parent(s)/LAR(s) should be redirected to the proper location to receive this care (e.g., Emergency Room) and an assessment visit could be scheduled to take place there at a suitable time.
- During the assessment visit, the investigator/study staff will evaluate the clinical signs and symptoms of the RTI. Signs and symptoms to be recorded in the eCRF are listed in the SPM.
- Oxygen saturation will be measured by pulse oximetry in room air using standardized equipment in preference.
- Specimen for testing of RSV and RVP at a local routine laboratory will be collected for all the subjects who have symptoms of an RTI.
- Nasal swabs for analysis at sponsor laboratory will be collected for all the subjects who have symptoms of an RTI. Note: all subjects experiencing an RSV-LRTI must be reported as an SAE in an expedited manner (refer to Section 9.4).
- Parent(s)/LAR(s) will be instructed to contact the study staff if the severity of the already existing symptoms increases or if the subject develops difficulty in breathing or wheezing and this may lead to a repeat assessment visit upon the judgment of the investigator.
- During subsequent surveillance contacts after an assessment visit, the status and evolution of the case will be followed until case resolution.
- Each assessment visit will be encoded in the eCRF.

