
If in the investigator's judgment a deterioration in the clinical status has occurred during the same RTI episode, then the most extreme value of all deteriorated clinical symptoms and signs (as listed in Part 2a and 2b) must be captured
 
N.B. May be completed in part or in full for any child experiencing a deterioration during the course of a disease episode
																												
Maximum temperature***		Record temperature and route of measurement																										
Maximum respiratory rate***		Breaths per minute counted over one minute																										
Lower chest wall indrawing (subcostal recession)***		Yes/No/Not available																										
Minimum SpO2 recorded***		% measured in room air (NB altitude is collected for each participating site)																										

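### Section 9.2.4 leaves a repeat visit to discretion, with no time limit, when an already-assessed infant develops breathing difficulty or wheeze, in conflict with the 24-hour visit in 9.2.1 and 9.2.3

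*Protocol*

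**What the plan says.** Section 9.2.4 deals with infants who have already had an assessment visit. Parents are told to call if existing symptoms get worse or if the infant "develops difficulty in breathing or wheezing and this may lead to a repeat assessment visit upon the judgment of the investigator". One sentence covers both triggers, and no deadline is attached.

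The two surveillance sections set a duty for the same symptoms:

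- Section 9.2.1 (calls from parents): in the event of "any new difficulty in breathing, wheezing or parental concern, the investigator/study staff will schedule an assessment visit as soon as possible", with a limit of 24 hours after the phone contact.
- Section 9.2.3 (contacts by staff): in the event of "any new or on-going difficulty in breathing, wheezing or parental concern, the investigator/study staff will schedule an assessment visit as soon as possible", with the same 24-hour limit.

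Section 1.2.4.1 restates the rule by reference to section 9.2: subjects with RTI symptoms are reviewed as soon as possible, and "those based on any suspicion of difficulty in breathing, wheezing or parental concern seen within 24 hours".

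Other text bears on an infant who deteriorates. Appendix D Part 3 applies where the investigator judges that the same episode has worsened, and says that "the most extreme value of all deteriorated clinical symptoms and signs (as listed in Part 2a and 2b) must be captured". Figure 3 footnote 6 reads "In case of worsening of symptoms, optional sample if the previous specimen was RSV-positive, and mandatory if the previous sample was RSV-negative". Section 9.2.4 adds that, at later surveillance contacts, "the status and evolution of the case will be followed until case resolution".

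**The concern.** An infant is assessed for a runny nose. Two days later the parent calls to report new difficulty in breathing. Under 9.2.1 a visit is due within 24 hours. Under 9.2.4 it is the investigator's choice, at no fixed time. A site can follow either section and believe it complies.

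Two things are at stake. The first is safety: the protocol describes this as the first use of the vaccine in infants likely to be unexposed to RSV, and progression from a cold to lower-airway signs is what the surveillance has to catch. The second is measurement: Table 6 grades each illness on its lowest SpO2 and highest respiratory rate. A value never taken cannot count, so an RSV-LRTI or severe RSV-LRTI may be graded too low in the group rates of section 11.10 and in the monthly IDMC reports of section 9.10.3, which use Table 6.

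**Working it through.** The conflict is one of text, so the provisions are set side by side first.

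| Provision | Who is covered | Trigger | Duty | Time limit |
|---|---|---|---|---|
| 9.2.1 | all subjects, parent calls | new difficulty in breathing, wheezing, parental concern | visit required | 24 hours |
| 9.2.3 | all subjects, staff contacts | the same, new or on-going | visit required | 24 hours |
| 9.2.4 | infants already assessed | worse existing symptoms, or difficulty in breathing or wheezing | investigator's judgment | none |
| Appendix D Part 3 | episodes judged to have deteriorated | deterioration | worst values recorded | none |
| Figure 3 footnote 6 | worsening | worsening | sample mandatory if the previous one was RSV-negative | none |

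**Do 9.2.1 and 9.2.3 reach an already-assessed infant?** Yes, on their wording. Section 9.2.1 opens by telling all parents to call for worsened as well as new RTI symptoms, which presupposes some infants who are already ill. Section 9.2.3 includes on-going difficulty in breathing. Neither section carves out infants already seen, and 9.2.4 does not say that it overrides them.

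**What do the other provisions leave open?** Part 3 records a one-minute respiratory rate, SpO2 in room air and a swab, observed by qualified staff, so it needs someone to see the infant. It starts, however, only once the investigator judges that deterioration has occurred. Footnote 6 likewise starts from worsening. Active contacts are by phone or e-mail and measure neither SpO2 nor respiratory rate. Section 9.2.5 covers admitted infants. What remains is a non-hospitalized infant with newly reported breathing difficulty who is not re-examined.

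**How much could one such infant matter?** The documents give no frequency, so the figures below are illustrations and not estimates.

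- Planned infections per RSV vaccine group (section 11.4): 50 × 0.5 × 0.2 = 5 with negative exposure status. This reproduces the protocol's figure.
- Entire Exposed Set, assuming the same 20% infection rate: 50 × 0.2 = 10.
- Progression not measured in an infant already counted as infected: the numerator falls by 1.
- Case lost because the re-swab after an RSV-negative sample was not taken: numerator and denominator both fall by 1.

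Exact (Clopper-Pearson) two-sided 95% intervals:

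| Situation | Of 5 infections | Of 10 infections |
|---|---|---|
| Two progressions, both measured | 2/5 = 40% (5.3% to 85.3%) | 2/10 = 20% (2.5% to 55.6%) |
| One not measured | 1/5 = 20% (0.5% to 71.6%) | 1/10 = 10% (0.3% to 44.5%) |
| One lost through a missed re-swab | 1/4 = 25% (0.6% to 80.6%) | 1/9 = 11.1% (0.3% to 48.2%) |

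The drops are 20 and 15 points with 5 infections, and 10 and 8.9 points with 10. Any single lost case among so few infections would do the same. The table shows sensitivity, not likelihood.

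**The case against.** The best defence is that the sections can be followed together. A parent's call under 9.2.4 is itself a passive surveillance contact, so 9.2.1 already compels the 24-hour visit, and 9.2.4 merely adds a route for other worsening. That reading is possible and is probably what was meant. But 9.2.4 names difficulty in breathing and wheezing expressly and makes the visit a matter of judgment, so a site reading it alone would be misled.

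Second, the Figure 3 decision tree is not visible. Its footnote 6 shows that the figure deals with worsening, and the tree may settle the visit and its timing. This stands as a limit on the finding. Even so, the text of 9.2.4 would need to agree with the figure.

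Third, the protocol provides for worsening visits. This stands and narrows the gap considerably. Section 9.2 also asks staff to assess the need for intervention in any reported illness, though it prescribes no examination or deadline for doing so.

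Fourth, section 1.2.4.1 is a rationale that defers to 9.2, so it is not independent evidence. That is correct.

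A reader might go further and infer that one missed case could reverse the conclusion against the 80% benchmark in section 11.11, because the one-sided 95% upper bound is 81.1% for 2/5 and 65.7% for 1/5. The documents do not support this as a consequence. The benchmark concerns very severe RSV-LRTI: at ordinary altitude, SpO2 below 90%, inability to feed, or unresponsiveness. The infant would have to be neither re-examined nor admitted, and nothing in the protocol suggests that this is likely.

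**Conclusion.** The conflict between 9.2.4 and the 24-hour rule in 9.2.1 and 9.2.3 is real on the visible text and should be corrected. Its practical reach is narrow: a non-hospitalized infant with newly reported breathing difficulty whom the site, relying on 9.2.4, does not see again. For that infant the grading value in Table 6 may be missed, and practice may vary between sites. How often this would happen is unknown.

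Three limits apply. Very severe cases are less exposed, since such infants are more likely to be recognized or admitted. Expedited reporting of RSV-LRTI does not depend on the affected definitions: section 9.1.5.2 says the Table 6 case definition "should not be used for the purpose of reporting RSV-LRTI as an AE of special interest during the trial conduct", and these reports, based on clinical judgment and local testing, reach the IDMC within 48 hours of the sponsor becoming aware. And if the missed share is equal across arms, within-group rates fall but the relative risk is not biased. Investigators have no routine access to treatment allocation, so the text gives no reason to infer a differential loss.

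The conclusion assumes that the unseen Figure 3 tree does not already impose the 24-hour visit on assessed infants. If it does, what remains is a correction to the wording of 9.2.4.

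**What to change.** Amend 9.2.4 so that new difficulty in breathing, wheezing or parental concern reported after an assessment visit requires a repeat (worsening) visit within 24 hours of the contact, as in 9.2.1 and 9.2.3. At that visit, complete Appendix D Part 3 where values have deteriorated, and re-swab as Figure 3 footnote 6 requires. Parental concern must be included, because it triggers the same 24-hour rule; omitting it would leave part of the conflict in place. Keep investigator discretion only for worsening of existing cough, runny nose or blocked nose without parental concern. Align Figure 3 if its tree says otherwise.

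The cost is one sentence in 9.2.4, possibly a change to the figure, and some repeat visits. On their wording, 9.2.1 and 9.2.3 already require those visits.

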#### **9.2.5. Subject hospitalized for LRTI**

Subjects admitted to hospital and treated for an LRTI will be documented fully as SAEs. In addition, to establish the severity of the illness, the eCRF screen corresponding to the assessment visit will be completed as fully as possible from medical records. Signs and symptoms to be recorded in the eCRF are listed in the SPM, and include where available oxygen saturation in air. Study staff will collect a nasal swab for all the subjects who have been hospitalized with a RTI for analysis at sponsor laboratory. All subjects with clinical suspicion of LRTI must be tested for RSV and RVP using locally available test.

Study staff will also collect a blood sample to be stored at sponsor's laboratory for future assessment of mechanism of illness (potential ERD). This will be required to be done only for RSV-positive subjects using a locally available RSV test.

**9.3. Detecting and recording adverse events, adverse events of special interest and serious adverse events****9.3.1. Time period for detecting and recording adverse events, adverse events of special interest and serious adverse events**

All AEs starting within 30 days following administration of each dose of study vaccine (Day 1 to Day 30) must be recorded into the appropriate section of the eCRF, irrespective of intensity or whether or not they are considered vaccination-related.

The time period for collecting and recording SAEs will begin at the first receipt of study vaccine and will end at study conclusion. See Section [9.4](#) for instructions on reporting of SAEs.

All AEs/SAEs leading to withdrawal from the study will be collected and recorded from the time of the first receipt of study vaccine.

In addition to the above-mentioned reporting requirements and in order to fulfil international reporting obligations, SAEs that are related to study participation (i.e., protocol-mandated procedures, invasive tests, a change from existing therapy) or are related to a concurrent GSK medication/vaccine will be collected and recorded from the time the subject consents to participate in the study until she/he is discharged from the study.

The time period for collecting AEs of special interest (RSV-LRTI) will begin at the first receipt of study vaccine and will end at study conclusion. The time period for collecting AEs of special interest (spontaneous or excessive bleeding) will begin at the first receipt of study vaccine and will end 30 days after the last vaccination on Day 61. See Section [9.4](#) for instructions on reporting of AEs of special interest.

An overview of the protocol-required reporting periods for AEs, AEs of special interest and SAEs is given in [Table 19](#).

Table 19 Reporting periods for collecting safety information (Amended 1 August 2019)

Visit	SCR	V1	V2	V3	V4	V5	V6	V7 end of the 1 st RSV season	V8 end of the 2 nd RSV season		
Days	-30 to -1	1	7	8	30	31	37	38	60	61	121
Solicited local and general AEs											
Unsolicited AEs											
AEs/SAEs leading to withdrawal from the study											
AE of special interest (RSV-LRTI)											
AE of special interest (spontaneous or excessive bleeding)*											
SAEs**											
SAEs related to study participation (start at signature of informed consent form) or concurrent GSK medication/ vaccine											

**AE:** Adverse Event; **RSV-LRTI:** Respiratory Syncytial Virus-Lower Respiratory Tract Infection; **SAE:** Serious Adverse Event; **SCR:** Screening; **V:** Visit.

\* Subjects' parent(s)/LAR(s) will be instructed to contact the investigator/study staff if their child presents symptoms of spontaneous bleeding or easy bruising or if their child develops a rash, within 30 days after either vaccination, in order to detect any thrombocytopenic petechiae or purpura.

\*\* Each subject's parent(s)/LAR(s) will be instructed to contact the investigator immediately should they/the subject manifest any signs or symptoms they perceive as serious.

